8.2 Sample Size

Sample size calculation is assessed at per-patient analysis based on previous evidence by Xie et al 2022 (14) in which the detection rate of erosions and ulcers (common lesions in suspected Crohn disease) in AI-assisted reading was 11.5%, compared to 9% in standard reading (i.e. a difference of the two proportion around $D=2.5\%$). Considering a non-inferiority one side test for the difference between correlated proportions. with a non-inferiority margin $M= 0.02$, a type I error α of 0.05, a power $1-\beta$ of 80%, a difference of the two proportion $D=0.025$ and a plausible proportion of concordance on positive detection in both AIR and SR of 8%, the sample size needed to establish the non-inferiority of AI-reading with respect to Standard Reading is $N=164$ patients (i.e. 164 VCE). The size will be raised up to $N=180$ in order to take into account a potential dropout rate up to 10%. Details about the sample size computation can be found in Liu, J., et al. (19); and in PASS sample size software documentation at https://www.ncss.com/wp-content/themes/ncss/pdf/Procedures/PASS/Non-Inferiority_Tests_for_the_Difference_Between_Two_Correlated_Proportions.pdf).

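### Enrolling 180 patients preserves the required 164 only up to 8.9% dropout, not the 10% stated in Section 8.2; the discrepancy is minor.

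*Protocol*

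**What the plan says.** Section 8.2 of the protocol gives three linked figures.

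- The requirement: "the sample size needed to establish the non-inferiority of AI-reading with respect to Standard Reading is $N=164$ patients".
- The enrolment target and its purpose: "The size will be raised up to $N=180$ in order to take into account a potential dropout rate up to 10" per cent.
- The planning basis: a "non-inferiority one side test for the difference between correlated proportions", "a type I error α of 0.05" and "a power $1-\beta$ of 80" per cent.

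The section gives no inflation formula, does not say of which number the 10% is a share, and makes no further allowance. No other section of the protocol adds one.

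**The concern.** An allowance for dropout should ensure that the required number is still available after the stated loss. Dropout is ordinarily a share of those enrolled, so the required number is divided by one minus the dropout rate. The figure 180 does not come from that operation, and at the upper limit the protocol itself names, the evaluable number falls below the number the protocol says it needs.

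What is at stake is the accuracy of two published design figures, the enrolment target and the attrition it can absorb. A team that enrolled 180 and lost 10% would believe from the text that the requirement was met, when it would be two patients short. This is not a detail left to a statistical analysis plan: the protocol states the relation between the figures, and states it incorrectly.

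**Working it through.** **Inputs, all from Section 8.2.** Detection rates: "in AI-assisted reading was 11.5%, compared to 9% in standard reading". Joint positive detection 8%. Difference D = 0.025. Margin: "with a non-inferiority margin $M= 0.02". One-sided α = 0.05, power 80%. Required size 164, enrolment 180, dropout up to 10%.

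**Step 1: reproduce the 164.**

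- Positive on AI-assisted reading only: 0.115 − 0.08 = 0.035.
- Positive on standard reading only: 0.09 − 0.08 = 0.010.
- Standard deviation under the alternative: s1 = √(0.035 + 0.010 − 0.025²) = √0.044375 = 0.2107.
- Standard deviation under the null, from the restricted maximum-likelihood estimate with the difference fixed at −0.02: the standard-only proportion is 0.03968, so s0 = √(2 × 0.03968 − 0.02 − 0.02²) = 0.2428.
- n = [(z₀.₉₅ × s0 + z₀.₈₀ × s1) / (D + M)]² = [(1.645 × 0.2428 + 0.842 × 0.2107) / 0.045]² = 164.2.

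This matches the stated 164, so the benchmark is valid. A Wald variance gives 135.5 and does not match, so the restricted-MLE formula is taken as the one used.

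**Step 2: check the dropout allowance.**

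| Question | Calculation | Result |
|---|---|---|
| Patients left after 10% loss from 180 | 180 × 0.90 | 162, two below 164 |
| Largest loss that keeps 164 | (180 − 164)/180 = 16/180 | 8.9% |
| Enrolment needed for 10% loss | 164/0.90 = 182.2, rounded up | 183 |

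The next smaller target, 182, gives 182 × 0.90 = 163.8. Counted in whole patients, 18 losses out of 182 (9.9%) would just leave 164, so the enrolment gap is two or three patients depending on rounding. On either count 180 is too few for 10%.

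The figure 180 is close to 164 × 1.10 = 180.4, which adds 10% of the required number instead of allowing for a loss of 10% of those enrolled. That origin is an inference; the mismatch does not depend on it.

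**Step 3: the effect on power.** Formula power is Φ[((D + M)√n − z₀.₉₅ × s0) / s1].

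| Evaluable n | Formula power |
|---|---|
| 162 | 79.5% |
| 164 | 79.95% |
| 165 | 80.2% |

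The dropout step costs 79.95 − 79.5, about 0.5 percentage points. Formula power first passes 80% at 165, so the value just below 80% at 164 arises from writing 164.2 as 164.

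Exact multinomial power of the score test under the same assumptions is 84.09% at 162 and 84.25% at 164. Both exceed 80%, and they differ by about 0.2 points.

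**The case against.** The strongest case on the other side is about weight and wording.

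- **The denominator.** The text says only "a potential dropout rate up to 10" per cent and does not say of what. Sixteen extra patients are 16/164 = 9.8% of the required number, so 180 could be read as a margin of roughly 10% on 164. This does not rescue the statement. A dropout rate is normally a share of those enrolled, and the other reading needs a denominator that the text does not supply.
- **The size.** Two evaluable patients are 1.2% of 164, and three enrolled are 1.6% of 183. Section 8.2 itself treats the difference as approximate and the 8% concordance as plausible, so two patients lie well within the uncertainty of the inputs. This stands, and it is why the point is minor.
- **The use of the tolerance.** No stopping rule or analysis rule in the protocol depends on it. The primary endpoint (Section 6.1) compares two readings of the same recorded video, so a missed 6- or 12-month visit (Section 7) would not by itself remove a patient from that comparison. This also stands: the protocol does not show that a 10% loss is likely for the primary endpoint.

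A reader might infer that the shortfall is what takes power below the planned 80%. The figures do not support that. On the formula, power is already 79.95% at 164 with no shortfall at all, and exact score-test power stays above 80% at both sizes.

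**Conclusion.** Wrong as written, minor. With 164 required, 180 covers dropout up to 8.9% (16 patients) and not 10%. At 10% loss the trial would have 162 evaluable patients, two short, at a cost of about 0.5 points of formula power.

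The conclusion takes dropout as a share of those enrolled and accepts the protocol's 164 as the benchmark. The power figures also rest on the stated detection rates, concordance and margin, whose suitability is not judged here.

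It would go too far to conclude that the primary analysis is endangered or that more patients must be recruited. The loss of power is too small for that.

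**What to change.** In Section 8.2, keep N = 180 and restate the dropout it covers as up to about 8.9%, or equivalently 16 patients. Adding that the rate is a share of those enrolled would remove the ambiguity.

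The cost is one changed figure and a slightly less favourable stated tolerance. No additional enrolment is needed, and no endpoint, margin or analysis changes. If the sponsor prefers to keep the 10%, the target becomes 183 (164/0.90), three more patients, but the size of the effect does not require this.

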9. PROJECT MANAGEMENT

The principal investigator will be responsible for the overall monitoring of data and the safety of study participants. The principal investigator will be assisted by other members involved in the study.

The investigators declare that they have no direct or indirect conflicts of interest.

10. POTENTIAL RISKS AND BENEFITS

There are no reasons to believe that enrolment in this study poses risks to the patient, as this is a prospective observational study involving the normal care activities of the patient, conducted according to GCP rules.

11. INSURANCE COVERAGE

Given the observational nature of the study and the absence of risks, no insurance coverage is provided.

12. ETHICAL ASPECTS

This study will be conducted in accordance with this protocol, the principles of good clinical practice, the ICH GCP regulations, and the requirements of the guidelines, following the principles of the Declaration of Helsinki (latest version: Tokyo, 2004 - Appendix I). The study protocol and all other necessary documents will be submitted to the Competent Authorities. The study will be submitted for approval to the relevant Territorial Ethics Committee. Amendments and new versions of the protocol will be promptly shared with the relevant Territorial Ethics Committee. This study will be conducted according to the protocol defined with the participating investigators. Participation in the study will be contingent upon obtaining informed consent.

13. PATIENT INFORMATION AND CONSENT

All patients will be invited to voluntarily participate in the study. They will be informed about the purpose of the study and the associated procedures. Patients will also have the opportunity to clarify any doubts or uncertainties by asking questions and receiving clear and satisfactory answers. After reviewing the study information, patients will have as much time as they need to decide whether to proceed with signing the informed consent form.

14. DATA MANAGEMENT AND STUDY DOCUMENT STORAGE

The data collected will be recorded, processed, managed, and stored in both paper and electronic formats exclusively for research purposes, in compliance with Legislative Decree No. 196 of June 30, 2003

(Code regarding the protection of personal data) and subsequent amendments, as well as in compliance with European Regulation No. 679 of 2016.

The Principal Investigator will be responsible for data management.

All information related to study participants, documentation regarding submission and approval by the relevant Ethics Committee, and regulatory documentation will be stored by the Research Manager, [name], at the archives of the Digestive Endoscopy Unit of the Fondazione Poliambulanza Istituto Ospedaliero in Brescia.

14.1. Data Confidentiality and Privacy

The privacy of the recruited subjects will be fully guaranteed, and the data will be processed confidentially in accordance with Italian law as outlined in Legislative Decree No. 196 of June 30, 2003, "Code regarding the protection of personal data" (Official Gazette No. 174 of July 29, 2003 – Ordinary Supplement No. 123) and in compliance with European Regulation No. 679 of 2016. Data collected during the study will be pseudonymized and processed solely for scientific purposes. Individual data will never be published but will be used exclusively, along with data from all other study patients, to produce descriptive and/or inferential analysis results. Each participating center must maintain adequate medical and research documentation for this trial and comply with regulatory/institutional requirements for the protection of study subjects' confidentiality. Data will be stored at the Digestive Endoscopy Unit of the Fondazione Poliambulanza Istituto Ospedaliero in Brescia and protected with specific security systems. Only specifically authorized personnel will have access.

14.2. Data Ownership

The ownership of the data related to the study, its execution, and its results belongs to the Fondazione Poliambulanza Istituto Ospedaliero (promoter and coordinator) (DL 30/11/2021).

15. POTENTIAL COSTS AND COVERAGE

No additional costs are expected beyond normal clinical practice. There is no funding provided for the study. The capsules used in the study will be supplied free of charge by the manufacturer. Due to the nature of the study, insurance coverage is not required.

16. DATA PUBLICATION

The results of the research will be made known to the public and to all interested parties through presentations at conferences and articles in scientific journals, preferably with international reach, without disclosing the identities of the patients.


1. First-degree relative with confirmed IBD
 
2. Gastrointestinal manifestations
 
 ○ Chronic diarrhoea (defined as more than 3 bowel movement per day and/or Bristol 6-7 stools for at least 3 months) ○ Chronic abdominal pain (at least 1 day/week in the last 3 months, typically not post-prandial) ○ Nocturnal symptoms ○ Blood and/or mucus in the stools ○ Non-healing or complex perianal fistula or abscess or perianal lesions (apart from haemorrhoids) 
3. Systemic manifestations
 
 ○ Weight loss (5% of usual body weight) in the last 3 months ○ Mild fever ($TC>37.5^{\circ}\text{C}$) in the last 3 months 
4. Laboratory findings
 
 ○ Fecal calprotectin $>100 \mu\text{g/g}$ ○ CRP $> 5 \text{ mg/dL}$ ○ Unexplained anemia (female Hb $< 11 \text{ g/dL}$; male Hb $< 13 \text{ g/dL}$) ○ Albumin $< 4 \text{ g/dL}$ ○ Iron deficiency (female ferritin $< 20 \text{ ng/mL}$; male $< 30 \text{ ng/mL}$) ○ B12 deficiency ($< 150 \text{ pg/mL}$) ○ Folate deficiency ($< 4 \text{ ng/mL}$) 	
1. First-degree relative with autoimmune disease
 
2. Extraintestinal manifestations
 
1. Musculoskeletal
 
 ○ arthritis (colitic type, ankylosing spondylitis, isolated joint involvement) ○ hypertrophic osteoarthropathy (clubbing, periostitis) ○ miscellaneous manifestations (osteoporosis, aseptic necrosis, polymyositis) 
2. Dermatologic and oral
 
 ○ reactive lesions (erythema nodosum, pyoderma gangrenosum, aphthous ulcers, necrotizing vasculitis) ○ specific lesions (fissures, fistulas, oral Crohn's disease, drug rashes) ○ nutritional deficiencies (acrodermatitis enteropathica, purpura, glossitis, hair loss, brittle nails) ○ associated diseases (vitiligo, psoriasis, amyloidosis) 
3. Hepatopancreatobiliary
 
 ○ primary sclerosing cholangitis ○ bile-duct carcinoma ○ associated inflammation (autoimmune chronic active hepatitis, pericholangitis, portal fibrosis, cirrhosis, granulomatous disease) 
4. Ocular
 
 ○ uveitis/iritis, episcleritis, scleromalacia, corneal ulcers, retinal vascular disease 
5. Renal
 
 ○ Calcium oxalate stones 
3. Systemic manifestations (malaise)
 
4. Laboratory findings
 
 ○ Vit.D deficiency ($< 20 \text{ ng/mL}$)

Figure 1

Nomenclature and semantic descriptions of ulcerative and inflammatory lesions in Crohn's disease of the small bowel in VCE modified from the international Delphi consensus statement

Nomenclature	Description
Aphthoid erosion*	Diminutive loss of epithelial layering (<5mm) with a whitish center and a red halo, surrounded by normal mucosa
Ulceration*	Mildly or frankly deep loss of tissue (>5mm) with a whitish base with or without edematous/swollen surrounding mucosa
Stenosis*	Narrowing of the intestinal lumen withholding or delaying the passing of the videocapsule
Edema	Enlarged / swollen / engorged villi
Hyperemia	Area of reddish villi
Denudation	Reddish (but not whitish) mucosal area where villi are absent

*significant inflammatory lesions reported during CE reading and considered for the statistical analysis

Figure 2

Lewis Score

Rated for each tertile					
Parameters	Number	Longitudinal extent		Descriptors	
Villous appearance	Normal	0	Short segment	8	Single
	Edematous	1	Long segment	12	Patchy
			Whole tertile	20	Diffuse
Ulcer	None	0	Short segment	5	<1/4
	Single	3	Long segment	10	1/4-1/12
	Few	5	Whole tertile	15	>1/2
	Multiple	10			
Stenosis – rated for whole tertile					
	None	0	Ulcerated	24	Traversed
	Single	14	Non-ulcerated	2	Not traversed
	Multiple	20			

Lewis score: Score of the worst-affected tertile [(villous parameter × extent × descriptor) + (ulcer number × extent × size)] + stenosis score (number × ulcerated × traversed).
